### 10.2.2 Renal safety monitoring

Once a participant is exposed to study treatment, the following two categories of abnormal renal laboratory alert values should be assessed during the study period:

- Serum creatinine increase  $\geq 25\%$  compared to screening during normal hydration status
- Any one of the following:
  - Urine protein-creatinine ratio (PCR)  $\geq 1$  g/g or  $\geq 100$  mg/mmol, OR
  - New onset dipstick proteinuria  $\geq 3+$ , OR
  - New onset dipstick hematuria  $\geq 3+$  (after excluding menstruation, UTI, extreme exercise, or trauma)

Abnormal renal event findings must be confirmed within 24-48 hours after the first assessment.

Once a participant is exposed to study treatment, renal laboratory alerts or renal safety events should be monitored and followed up by the investigator or designated trial staff as summarized in [Section 16.3](#). Additional details on actions required in case of renal events are outlined in [Table 16-4](#) and [Table 16-5](#).

### 10.2.3 Adverse Events of Special Interest

Avoiding exposure to the relevant allergens is a cornerstone of the standard of care for management of food allergy. Nonetheless, accidental exposures and subsequent food allergy reactions are known to occur. These adverse events are of special interest because they relate to the primary outcome, which is increase in the eliciting dose of known food allergen. This study will collect data regarding all likely food allergy reactions.

Additional adverse events of special interest related to remibrutinib, CCI will be collected also.

### 10.2.4 Hematologic safety monitoring

Once a participant is exposed to study treatment, hematologic laboratory alert values should be assessed during the study period:

Discontinuation of the study treatment should be considered if the abnormal hematology parameter is confirmed:

- Hemoglobin:  $< 10$  g/dl
- Platelets:  $< 75\,000/\text{mm}^3$
- Leukocytes:  $< 3\,000/\text{mm}^3$
- Neutrophils:  $< 1\,500/\text{mm}^3$

Abnormal hematologic laboratory findings must be confirmed within 24-48 hours after the first assessment.

Once a participant is exposed to study treatment, hematologic laboratory alerts or hematologic safety events (e.g., significant bleeding) should be monitored and followed up by the investigator or designated trial staff as summarized in [Section 16.1](#).

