- Response to vaccination:** CCI [REDACTED]

[REDACTED]

[REDACTED]

[REDACTED]

[REDACTED]

[REDACTED]

[REDACTED]

[REDACTED]
- Effect on platelet function - risk for bleeding:** BTK is a signaling kinase in one of several platelet activation pathways. In patients with B cell malignancies (chronic lymphocytic leukemia, Waldenström's macroglobulinemia, mantle cell lymphoma) treated with the BTK inhibitors ibrutinib or acalabrutinib, major bleeding events (i.e. serious events, gastrointestinal bleeding) were reported. However, the underlying hemato-oncologic diseases of these patients, the prevalence of anti-coagulant/anti-platelet comedication use and the association with such complications should be taken into consideration. No relevant increase in bleeding risk has been observed in patients with X-linked agammaglobulinemia, an inborn genetic deficiency of BTK (Quek et al 1998, Futatani et al 2001). Furthermore, BTK inhibition does not have any impact on the plasmatic coagulation system, and plasmatic coagulation was not affected in the human Phase 1 study up to the highest tested dose of CCI [REDACTED] remibrutinib. In the completed and ongoing trials with remibrutinib, only a few mild and moderate bleeding events were reported. In the primary analysis of the Phase 2b study CLOU064A2201, 13 (4.9 %) non-serious bleeding events were reported on any remibrutinib dose compared to one event on placebo (2.4 %). None of the events reported on remibrutinib was serious or severe. There was a single mild event (gingival bleeding) leading to treatment discontinuation. Participants receiving remibrutinib are closely monitored for any signs and symptoms of bleeding while in the trial. Blood cell counts (including thrombocytes),

inclusion/exclusion criteria, study procedures, very close clinical and laboratory monitoring, and study drug discontinuation rules. As with investigational drugs in general, not all safety risks are known. Participants and investigators participating in this trial will be informed should important new safety information become available.

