### **6.2.1 Concomitant therapy**

All medications, procedures, and significant non-drug therapies (including physical therapy and blood transfusions) administered after the participant was enrolled into the study must be recorded on the appropriate eCRF.

Each concomitant drug must be individually assessed against all exclusion criteria, medication allowed under certain conditions (listed in [Table 6-2](#)) and prohibited medication (listed in [Table 6-3](#)). If in doubt, the investigator should contact Novartis before randomizing a participant or allowing a new medication to be started. If a participant is already enrolled and taking a prohibited medication, the investigator should contact Novartis to determine if the participant should continue in the study.

Remibrutinib has been extensively investigated with respect to potential drug-drug interactions (DDI) as victim or perpetrator. As these interactions may lead to significant changes in the exposure of remibrutinib or respective co-medications some drugs are either prohibited or co-administration requires action and must be used with caution.

Oxidative metabolism is the major clearance pathway of remibrutinib and predominantly mediated by CYP3A4 with only minor contribution of other clearance pathways. Therefore, at doses investigated in this study co-administration of strong and moderate CYP3A4 inhibitors are prohibited in this study. Concomitant administration of moderate and strong inducers of CYP3A4 is also prohibited during the study (see [Table 6-4](#)). Remibrutinib has been shown in vitro to inhibit some efflux and uptake transporters [such as P--glycoprotein, OATP1B, MATE-1, OAT3, organic cation transporter 1 and breast cancer resistance protein (BCRP)]. Therefore, concomitant administration of remibrutinib with respective BCRP substrates with a small safety margin may be administered with caution (see [Table 6-3](#)).

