## **9 Discontinuation and completion**

### **9.1 Discontinuation from study treatment and from study**

#### **9.1.1 Discontinuation from study treatment**

Discontinuation of study treatment for a participant occurs when study treatment is stopped earlier than the protocol planned duration and can be initiated by either the participant or the investigator. The investigator must discontinue study treatment for a given participant if he/she believes that continuation would negatively impact the participant's well-being.

Study treatment must be discontinued under the following circumstances:

- Participant decision
- Pregnancy
- Any SAE, with the exception of anaphylaxis unrelated to study drug, and which does not require hospital admission for  $\geq 24$  hours.
- Any severe AE that is assessed to be at least possibly related to study drug
- Any moderate to severe infection
- Participant requires use of prohibited treatment as per [Section 6.2.2](#)
- Participant failure to comply with the study protocol results in potential risk to the participant
- Participant experiences a moderate or severe hypersensitivity event unrelated to the DBPCFC and suspected to be related to study treatment
- Confirmed QTcF  $> 500$  msec
- Abnormal liver laboratory results requiring discontinuation (see [Section 16.2](#))
- Abnormal renal laboratory results requiring discontinuation (see [Section 16.3](#))
- Platelets  $< 75,000/\text{mm}^3$
- Clinically significant spontaneous bleeding events
- Any other adverse event or laboratory abnormality that in the judgment of the investigator prevents the participant from safely continuing in the study
- Any protocol deviation or other situation that results in a significant risk to the participant's safety

If discontinuation of study treatment occurs, the investigator should make a reasonable effort to understand the primary reason for the participant's premature discontinuation of study treatment and record this information. If treatment code has been broken as noted in [Section 6.5](#) and [Section 6.7.3](#), and site personnel and sponsor determine discontinuation of study treatment is indicated, this information should be recorded. The investigator must also contact the IRT to register the participant's discontinuation from study treatment.

**All participants who discontinue from study treatment prematurely should complete the End of Study visit at the time of treatment discontinuation.**

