## 16 Appendices

### 16.1 Appendix 1: Clinically notable laboratory values and vital signs

The following specific criteria have been identified for this study. Should these criteria be met, a re-test must be done within 5 days after the first assessment. Discontinuation of the study treatment should be considered if the abnormal hematology parameter is confirmed:

- Hemoglobin: < 10 g/dl
- Platelets: < 75 000/mm^3
- Leukocytes: < 3 000/mm^3
- Neutrophils: < 1 500/mm^3

For all other laboratory assessments, the central laboratory will flag laboratory values falling outside of the normal ranges on the central laboratory report (which the investigator should review and sign-off) and the investigator will report any values considered clinically significant in the eCRF.

Refer to [Section 16.2](#) for clinically notable laboratory values for hepatotoxicity.

Refer to [Section 16.3](#) for clinically notable laboratory values for nephrotoxicity.

For ECGs, a notable QTc value is defined as a QTc (Fridericia's) interval of greater than 450 msec for males or greater than 460 msec for females – all such ECGs will be flagged by the central CRO's cardiologist and require assessment for clinical relevance by the investigator. Confirmed QTcF > 500 msec requires discontinuation of study treatment.

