## 5.2 Laboratory parameters derivations

Refer to Section 16.2 of the protocol for clinically notable laboratory values for hepatotoxicity.

Refer to Section 16.3 of the protocol for clinically notable laboratory values for nephrotoxicity

- Discontinuation of the study treatment should be considered if the abnormal hematology parameter is confirmed: Hemoglobin: < 10 g/dL
- Platelets: < 75 000/mm^3
- Leukocytes: < 3 000/mm^3
- Neutrophils: < 1 500/mm^3

For all other laboratory assessments, the Central Laboratory will flag laboratory values falling outside of the normal ranges on the Central Laboratory Report (which the investigator should review and sign-off) and the investigator will report any values considered clinically significant in the CRF.

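### Platelets below 75,000/mm³, needed CYP3A4 drugs and, narrowly, confirmed serious infection carry a mandatory stop in Protocol 9.1.1 and 6.2.2 but only discretionary action elsewhere

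*Protocol*

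**What the plan says.** **Platelets.** Protocol 9.1.1 opens its list with "Study treatment must be discontinued under the following circumstances", and platelets below 75,000/mm³ are on it. The QTcF item in that list needs a confirmed value; the platelet item carries no such qualifier. Protocol 10.2.4 names the same threshold, alongside hemoglobin, leukocytes and neutrophils, under "Discontinuation of the study treatment should be considered if the abnormal hematology parameter is confirmed". It adds "Abnormal hematologic laboratory findings must be confirmed within 24-48 hours after the first assessment". Protocol 16.1 repeats the soft rule, with the instruction that "a re-test must be done within 5 days after the first assessment". SAP 5.2 carries the soft rule too: "Discontinuation of the study treatment should be considered if the abnormal hematology parameter is confirmed: Hemoglobin: < 10 g/dL", followed by the platelet, leukocyte and neutrophil limits.

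**CYP3A4 drugs.** Protocol 6.2.1 states that "co-administration of strong and moderate CYP3A4 inhibitors are prohibited in this study", and extends the prohibition to moderate and strong inducers. Section 6.2.2 requires study treatment and the food challenge (DBPCFC) to stop if a prohibited drug becomes necessary; 9.1.1 repeats the treatment stop. In Appendix 6, the action columns say something else. For moderate and strong inhibitors and for moderate inducers, the drug is to be avoided where an alternative exists. For strong inducers, it is to be stopped where that is medically justifiable, with monitoring.

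**Infection.** Protocol 9.1.1 requires discontinuation for a moderate to severe infection and for any SAE, apart from a limited anaphylaxis exception. Section 16.1.1 asks the investigator to consider interrupting the drug when a serious or atypical infection is suspected or confirmed.

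**The concern.** The same finding in the same participant leads to different actions depending on which page the site has open. The protocol gives no explicit order of precedence.

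The protocol itself shows why the stricter text matters. Section 4.5 lists bleeding as a potential risk of the drug, on the ground that "BTK is a signaling kinase in one of several platelet activation pathways". Section 6.2.2 puts the rise in exposure with CYP3A4 inhibitors at up to 4-fold. It cites a model that predicts a 90% fall with inducers, with possible complete loss of efficacy. A participant left on an inducer could then face an end-of-treatment peanut challenge with little drug on board.

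The choice of text also affects who is challenged. Under 9.1.1, a participant who discontinues treatment has no further DBPCFC and so is not a completer for the primary analysis.

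**Working it through.** The plan states no figure to reproduce. The check compares the action attached to each trigger in the current text.

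| Trigger | Mandatory text | Softer text | Does following the softer text satisfy the mandatory one? |
|---|---|---|---|
| Platelets <75,000/mm³ | 9.1.1: stop | 10.2.4, 16.1, SAP 5.2: consider stopping if confirmed | No, if the site considers it and continues |
| Hemoglobin, leukocytes, neutrophils | None specific in 9.1.1 | 10.2.4, 16.1, SAP 5.2: consider stopping if confirmed | No conflict |
| Moderate or strong CYP3A4 inhibitor, or moderate inducer, needed | 6.2.1, 6.2.2: prohibited; 6.2.2, 9.1.1: stop treatment (6.2.2 also the DBPCFC) | Tables 16-8, 16-9: avoid if there is an alternative | No, if there is no alternative |
| Strong CYP3A4 inducer needed | As above | Table 16-9: stop the inducer if medically justifiable, and monitor | No, if stopping it is not justifiable |
| Confirmed serious infection | 9.1.1: stop, through the SAE item | 16.1.1: consider interruption | No, if the site considers it and continues |
| Suspected infection, not yet confirmed | Not clearly triggered | 16.1.1: consider interruption | No clear conflict |
| Moderate, non-serious, typical infection | 9.1.1: stop | 16.1.1 does not address it | No conflict |

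The mismatch runs one way. A site that stops satisfies both texts; a site that uses the discretion in the softer text breaches the mandatory one.

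**Re-test limits.** A repeat at 24-48 hours also falls within 5 days, so both limits can be met. They are untidy, not contradictory.

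**Size per event.** Inputs: 72 randomized at 2:2:2:1:1 (Protocol 12.8), so the ratio has 8 parts.

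- One-month remibrutinib arm: 72 × 2/8 = 18; one participant is 1/18 = 5.6%.
- Placebo arm: 72 × 1/8 = 9; one participant is 1/9 = 11.1%.

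Randomized numbers are the right base, because someone stopped before the challenge was never a completer. These are shares per event, not forecasts. A lost challenge is also not certain in every case: 6.7.1 and 9.1.2 let a participant who stopped for an adverse event, resumed and met the dosing limits go on to the DBPCFC.

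**The case against.** The best reply is that the softer texts rank lower. Protocol 4.5 describes the 16.1 material as recommended guidelines, 6.7.2 labels 16.1 and 16.1.1 as guidance, and considering a stop does not forbid one. This weakens the appendix conflicts, especially infection. It does not reach 10.2.4, which is body text. Nor do those two sections cover Tables 16-8 and 16-9, whose wording still permits what 6.2.2 forbids.

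A reader might infer more than the documents support:

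- **That the sponsor may keep someone on study drug with a prohibited medicine.** Section 6.2.1 says "the investigator should contact Novartis to determine if the participant should continue in the study". The glossary separates leaving the study from stopping study treatment, so a participant stopped under 6.2.2 can remain for follow-up. The two sentences are compatible.
- **That cimetidine is cleared for use.** Table 6-2 names it as an example and Table 16-8 lists it as a moderate inhibitor. But 6.2.1 requires each drug to be checked against the exclusion criteria and the prohibited list as well. It is a poor example, not a permission.
- **That rifabutin and phenobarbital have two governing rules.** They appear in both Table 16-8 and Table 16-9 with different actions, but moderate and strong inducers are prohibited alike, so the label changes nothing.
- **That the trial's power is at risk.** Section 12.8 already allows for about 10% discontinuation, and 5.2 excludes platelets below 100,000/mm³ at screening.

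Table 6-4 is redacted, so its relation to Appendix 6 cannot be checked. The CYP3A4 point therefore rests on the text of 6.2.1, 6.2.2 and 9.1.1, which is explicit.

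**Conclusion.** The point holds for platelets below 75,000/mm³ and for the action columns of Tables 16-8 and 16-9, and narrowly for confirmed serious infection. The last assumes that serious in 16.1.1 has its regulatory meaning, so that the event is an SAE. That 9.1.1 and 6.2.2 should govern is a recommendation: the documents do not state it, but these sections use mandatory language and 6.2.2 gives its reasons.

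The gain is consistent participant safety. The documents give no frequency for any of the triggers, so no number of affected participants is claimed, and the effect on the primary analysis is likely small. Within the SAP, the one analysis question found is a cimetidine user. Deviation code COMD01 in SAP 2.5.4 draws on Tables 6-4 and 6-2, so it is unclear whether that person's challenge result is kept or set to missing in one sensitivity analysis.

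This should be corrected, but it does not undermine the design.

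**What to change.** By protocol amendment, with a text correction to SAP 5.2:

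1. **Platelets.** Keep them in the 10.2.4 and 16.1 lists, because those lists trigger the alert and re-test, and use one 24-48 hour limit in both. State there and in SAP 5.2 that platelets below 75,000/mm³ require discontinuation per 9.1.1, so that the discretionary wording covers only hemoglobin, leukocytes and neutrophils. If confirmation is intended, 9.1.1 should say that drug is held pending the 24-48 hour re-test and discontinued if the value is confirmed.
2. **CYP3A4.** Replace the action columns of Tables 16-8 and 16-9 with *prohibited; see 6.2.2*. Remove cimetidine from the Table 6-2 examples. Correct the prohibited-medication reference in 6.2.1 from Table 6-3 to Table 6-4. Nothing else in 6.2.1 needs to change.
3. **Infection.** Add to 16.1.1 that infections meeting 9.1.1 (moderate to severe, or an SAE) require discontinuation and that the option to consider interruption does not override it. Do not add a confirmation requirement to the 9.1.1 infection rule, which would soften it.

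**Cost.** A wording amendment needs IRB/IEC approval and, where required, health authority approval (Protocol 14.1). No assessments are added, and no mandatory stop beyond those in 9.1.1 and 6.2.2. Participants lose cimetidine; the other H2 antagonists named in Table 6-2 remain. The SAP was last updated in May 2025, before final database lock. If dosing has already ended, what remains useful is the SAP 5.2 correction, a decision on cimetidine under COMD01, and cleaner text for later protocols.

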## **11 Data Collection and Database management**

### **11.1 Data collection**

Designated investigator staff will enter the data required by the protocol into the eCRFs. The eCRFs have been built using fully validated secure web-enabled software that conforms to 21 CFR Part 11 requirements. Investigator site staff will not be given access to the EDC system until they have been trained. Automatic validation programs check for data discrepancies in the eCRFs, allow modification and/or verification of the entered data by the investigator staff.

The investigator/designee is responsible for assuring that the data (recorded on eCRFs) is complete, accurate, and that entry and updates are performed in a timely manner. The Investigator must certify that the data entered are complete and accurate.

After final database lock, the investigator will receive copies of the participant data for archiving at the investigational site.

All data should be recorded, handled, and stored in a way that allows its accurate reporting, interpretation, and verification.

### **11.2 Database management and quality control**

Novartis personnel (or designated CRO) will review the data entered by investigational staff for completeness and accuracy. Electronic data queries stating the nature of the problem and requesting clarification will be created for discrepancies and missing values and sent to the investigational site via the EDC system. Designated investigator site staff are required to respond promptly to queries and to make any necessary changes to the data.

Concomitant treatments and prior medications entered into the database will be coded using the World Health Organization (WHO) Drug Reference List, which employs the Anatomical Therapeutic Chemical classification system. Medical history/current medical conditions and adverse events will be coded using the Medical Dictionary for Regulatory Activities (MedDRA) terminology.

Dates of screenings, randomizations, screen failures and study completion, as well as randomization codes and data about all study treatment (s) dispensed to the participant and all dosage changes will be tracked using an Interactive Response Technology (IRT). The system will be supplied by a vendor, who will also manage the database. The data will be sent electronically to Novartis (or a designated CRO) at specific timelines.

Each occurrence of a code break via IRT will be reported to the clinical team and monitor. The code break functionality will remain available until study shut down or upon request of Novartis.

Once all the necessary actions have been completed and the database has been declared to be complete and accurate, it will be locked and the treatment codes will be unblinded and made available for data analysis. Any changes to the database after that time can only be made after written agreement by Novartis development management.

### **11.3 Site monitoring**

Before study initiation, at a site initiation visit or at an investigator's meeting, a Novartis representative will review the protocol and data capture requirements (i.e. eCRFs) with the investigators and their staff. During the study, Novartis employs several methods of ensuring protocol and GCP compliance and the quality/integrity of the sites' data. The field monitor will visit the site to check the completeness of participant records, the accuracy of data capture/data entry, the adherence to the protocol and to Good Clinical Practice, the progress of enrollment, and to ensure that study treatment is being stored, dispensed, and accounted for according to specifications. Key study personnel must be available to assist the field monitor during these visits. Continuous remote monitoring of each site's data may be performed by a centralized Novartis/delegated CRO/CRA organization. Additionally, a central analytics organization may analyze data & identify risks & trends for site operational parameters, and provide reports to Novartis clinical teams to assist with trial oversight.

The investigator must maintain source documents for each participant in the study, consisting of case and visit notes (hospital or clinic medical records) containing demographic and medical information, laboratory data, electrocardiograms, and the results of any other tests or assessments. All information on eCRFs must be traceable to these source documents in the participant's file. The investigator must also keep the original informed consent form signed by the participant (a signed copy is given to the participant).

The investigator must give the monitor access to all relevant source documents to confirm their consistency with the data capture and/or data entry. Novartis monitoring standards require full verification for the presence of informed consent, adherence to the inclusion/exclusion criteria, documentation of SAEs, and of data that will be used for all primary variables. Additional checks of the consistency of the source data with the eCRFs are performed according to the study-specific monitoring plan. No information in source documents about the identity of the participants will be disclosed.

